## **STUDY ENDPOINTS**

This is a mechanistic study; therefore, the main study aim is to show that the hippocampal stimulation leads to functional connectivity changes across series of hippocampal networks and how these connectivity changes are correlated with pain decrease.

The secondary outcome will be changes in pain ratings. The effects of the brain stimulation will be measured by daily pain ratings (painApp) and questionnaires, using our in-house pain app. As we collect these outcomes repeatedly, we will have changes in pain immediately after the stimulation session and also over the next 2-weeks. We will test immediate and 2-weeks changes in painApp ratings relative to baseline. Questionnaire analyses, and other time course analyses of painApp data will be treated as exploratory in nature.

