### **MRI Scan:**

Subjects will undergo MRI scanning at the Northwestern University, Department of Radiology Center for Translational Imaging (CTI). All procedures are standard in our laboratory and have been approved in multiple previous IRB protocols.

More specifically, we will conduct a MRI scan (Siemens Trio, 3T, 64-channel head coil) with both structural (T1 scan, 5 minutes) and rsfMRI (EPI scan, 8 minutes) protocols. No contrast will be used in the MRI.

The structural scan will allow us to use the built-in neuronavigation TMS system, for optimal localization of the stimulation sites. Resting-state fMRI will be used to identify the functional localization for indirect stimulation of the hippocampus. To do so, we will follow a well-established in-house processing pipeline, replicating the methods used in our previous experiments using this method . Briefly, whole-brain seed-based correlation will be performed, using the left dorsal hippocampus as a seed region. This will allow us to identify, at a single-subject level, the exact parietal target that has maximal connectivity to the dorsal hippocampus. By stimulating this parietal target, modulation of the hippocampus connectivity can be achieved non-invasively  and with long-lasting effects in brain connectivity after three stimulation sessions .

In this same visit, participants will further complete questionnaires regarding pain ratings and the characteristics of their pain (see below for detail information).

Participants will be assigned to one of the six possible stimulation sequences and trained on our pain app (a smartphone-based tool used to rate pain and mood on NRS scales, as well as indicate rescue medication use, twice a day). They will be asked to use the pain app for the next 7-10 days prior to the first round of intervention and during all the study duration.

STU#:

There will be 2 MRI visits: one at baseline (visit 1), the second MRI will depend on participants allocation: participants randomized to group 1 will have a second MRI at visit 6; and participants randomized to group 2 at visit 11.

- **Visit 2 – 11** (Approx Time: 1 hour)

Intervention visits: These visits will be scheduled ~1 week after the visit 1 measurements are done.

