At visit 2, the stimulation protocol will start, and participants will receive a total of 10 sessions: 5 consecutive daily sessions of each stimulation round following the prior stimulation sequence order, interleaved by 2 weeks of wash out period. All subjects will undergo sessions of sham, and hippocampal-stimulation, in a crossover manner. As different stimulation conditions (hippocampal, M1 or sham) will be delivered in each of the two rounds of stimulation, participants will be told that stimulations can feel and sound different.

Before stimulation, the subjects will complete the following assessments:

- NRS for back pain

After each session, subjects will complete the following assessments:

- Side Effects Questionnaire for rTMS
- NRS for back pain
- At visits 6 and 11 participants will also complete the following questionnaires:
  - PainDetect;
  - Short-form Montreal Pain Questionnaires (sfMPQ);
  - BDI

Global impression of changeAfter the end of Round 1 or Round 2:

- MRI

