Demographic survey and patient information criteria	X		
Pregnancy test (if applicable) 	X	X 	
Drug urine test	X		
Vitals measurements	X		
Personal Health History (PHH)	X		
General physical exam	X		
BDI	X		
MRI	X		X 
Pain Detect Questionnaire (Pdq)	X		X
Short-form Montreal Pain Questionnaires (sfMPQ)	X		X
Pain Catastrophizing Scale (PCS)	X		
NIH PROMIS-57 Profile	X		
Randomization	X		
rTMS stimulation		X	X
NRS before/after stimulation		X	X
NRS average pain			X
Adverse events questionnaire		X	X
PainApp (During all the study) 	X	X	X
Approximate visit duration	2-3 hrs	1-2 hrs	1-2 hrs

**Table 1:** Related Procedures and Study Schema. Visits 1 through 10 will be completed according to the presented schema. 1. There is no specific recommendation for or against pregnancy, however, since this study will be utilizing Repetitive TMS as a mode of intervention, we will take the conservative approach and exclude pregnancy. Female subjects of childbearing potential will be asked to take a pregnancy test. If the pregnancy test is positive, the subject may not enroll in the study. Pregnancy test will be repeated in visits 2 and 8 (every ~ 2 weeks).

STU#:

2. Visit 6 and 11: These visits will be separated in two parts: part 1: last day of stimulation (stimulation + questionnaires) and part 2: MRI (at least 24hrs after part 1). For group 1, only visit 6 will have 2 parts and for group 2 only visit 11 (see Figure 1 for details).
3. PainApp: participants will be instructed to use our smartphone-based app to report pain intensity (NRS, where 0 is no pain and 10 is worst imaginable pain), mobility (minimum, average, maximum), mood (NRS, where -10 is sad and +10 is happy), and medication use, collected twice daily from Visit 1 until the end of participation).

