## RISKS TO PARTICIPANTS

### Taking part in this study may involve the following risks:

The most common side effects of rTMS can include mild headaches or discomfort at the stimulation site. This occurs in approximately 5% of subjects. The subject is allowed to stop the stimulation at any time if they feel uncomfortable. These effects generally wear off shortly after the session and can be treated via over-the-counter analgesics. If subjects experience discomfort at a stimulation location, research staff will attempt to move the stimulator to a location that minimizes this discomfort. Research staff will be in constant contact with the subject during the rTMS procedure and will discontinue the protocol if discomfort cannot be successfully reduced. Vital signs will be collected and used to exclude subjects from rTMS if outside of normal established ranges (see above). With the permission of the subject, the primary care physician will be contacted by the research team to arrange follow-up care if vital signs are outside of the normal range.

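### Side effects are asked about only after each session, so washout events are first solicited after the other modality, and events after visit 11 or early withdrawal never are

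*Combined protocol and SAP*

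**What the plan says.** In the Visit 2 – 11 section, the "Side Effects Questionnaire for rTMS" is listed under "After each session, subjects will complete the following assessments". The only assessment listed before stimulation is a back-pain rating. In Table 1 the row "Adverse events questionnaire" is marked for visits 2 to 5 and 7 to 10 and for visits 6 and 11. It is not marked for visit 1, and the table has no column for the washout, the period after visit 11, or early withdrawal.

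On design, the same section states: "All subjects will undergo sessions of sham, and hippocampal-stimulation, in a crossover manner". The two rounds of five daily sessions are "interleaved by 2 weeks of wash out period". Study Timelines puts a two-week washout after each treatment period and gives total participation as about 7 weeks.

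On the expected course, Risks to Participants says of headache and site discomfort: "These effects generally wear off shortly after the session and can be treated via over-the-counter analgesics". Study Endpoints follows "changes in pain immediately after the stimulation session and also over the next 2-weeks".

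Withdrawal of Participants covers payment and the handling of incomplete data, and describes no safety contact. Compensation for Research-Related Injury has participants told to report illness or injury to the study doctor. The app description allows free entry of anything else the participant wants to mention.

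**The concern.** In a two-period crossover, an adverse event can be linked to a modality only if someone asks about it before the next modality starts, or if its onset date is recorded. Neither is provided for at the change of round. The form at visit 7 follows the first session of the other modality, and no recall period, onset-date field or rule for assigning events to a round is given. After the second round, no scheduled form asks at all. The same is true of participants who leave early, among whom poor tolerance may be over-represented.

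At stake is whether the pilot can describe the tolerability of active and sham stimulation by modality, including effects that begin or persist after the last session of a round. The Power Calculation section intends the results to inform a later treatment study, so that description has some value even though it is not an endpoint.

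**Working it through.** **Inputs.** Baseline app period 7–10 days (MRI Scan section); two rounds of 5 consecutive daily sessions with 2 weeks between them (Visit 2 – 11); 2 weeks after each round and about 7 weeks in total (Study Timelines); two app ratings a day, about 100 in all (Visit 1 procedures); form after each of 10 sessions (Visit 2 – 11, Table 1); 16 recruited for 12 completers (Power Calculation).

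**1. Reproduce the stated length.**
- With two weeks after visit 11: 7 + 5 + 14 + 5 + 14 = 45 days, or 10 + 5 + 14 + 5 + 14 = 48 days. That is 6.4–6.9 weeks and 90–96 ratings, which fits about 7 weeks and about 100 ratings.
- Without them: 31–34 days, or 4.4–4.9 weeks and 62–68 ratings, which does not fit.

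The two weeks after visit 11 are therefore part of participation.

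**2. Days with and without a form.** From first stimulation to end of participation: 5 + 14 + 5 + 14 = 38 days. Form days: 10. Days without a form: 38 − 10 = 28, and 28/38 = 74%. These are 14 days between rounds and 14 after visit 11.

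**3. Gap at the change of round.** With 14 full days between rounds, the visit 7 form comes 15 days after the visit 6 form. The protocol says only 2 weeks, so this depends on scheduling. If visit 7 falls 14 to 17 days after visit 6 (an assumption), the span from visit 2 to two weeks after visit 11 is 37–40 days, with 27–30 of them lacking a form (27/37 = 73%; 30/40 = 75%). The conclusion does not change.

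**4. Which sessions lack a next-day form.** Within a round, sessions 1 to 4 are each followed by another form the next day under the same modality: 4 × 2 = 8 of 10 sessions, if none is missed. The exceptions are the sessions at visits 6 and 11.

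**5. What happens to an event that starts after the fifth session of a round.**
- *Round 1:* the first scheduled question comes after the first session of the other modality.
  - If the form asks only about that day's session, the event is missed.
  - If it has open recall and no onset date, the event appears on a form attached to the other modality.
  - If it asks for onset, the event can be placed correctly, from about two weeks' memory.
- *Round 2:* no scheduled question follows.
- *Early withdrawal:* no scheduled question follows. The plan allows for 16 − 12 = 4 such participants.

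This applies equally to active and sham and to both sequences.

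**6. Other contacts in the gaps.** The second MRI, at least 24 hours after the last session, follows one round per participant; Table 1's footnote puts the questionnaires in the stimulation part of that visit. Staff query well-being during stimulation and scanning, which adds no time point in the washout. The app asks twice daily for pain, mood, mobility and medication use but lists no side-effect item. Medication changes are asked about at later visits.

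**The case against.** The strongest reply is that collection just after the session suits the risks the protocol describes: headache and site discomfort that resolve soon, and seizure during a session. The gaps are also not silent. Pain, mood and medication use are logged twice daily throughout, dated within the correct round, and participants are told to report illness or injury. This stands, and it limits the size of the problem. But these data are indirect, and neither spontaneous route asks about side effects or describes how a report becomes an adverse-event record.

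Four stronger readings are tempting and are not supported:

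- *Washout events will be filed under the wrong modality.* The form's content, recall period and any filing rule are not given. Misattribution is one possibility, omission another, and a form with onset dates could avoid the first.
- *The safety comparison of active with sham is compromised.* None is planned. Study Endpoints names connectivity and pain, and the Data Analysis Plan specifies only two analyses of app pain ratings.
- *The statement that effects wear off soon cannot be checked.* Next-day forms follow 8 of 10 sessions, so it can be checked in part.
- *The protocol itself expects delayed side effects, because stimulation acts "with long-lasting effects in brain connectivity after three stimulation sessions".* That phrase concerns connectivity, and the two-week follow-up concerns pain. Neither says that adverse effects are delayed.

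**Conclusion.** The gap is real and follows directly from the schedule. Events starting after the visit 6 session are first solicited about two weeks later, after the other modality has been given. Events after visit 11 or after early withdrawal are never solicited. About 74% of the days from first stimulation onward have no form (73–75% over the scheduling range shown).

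The harm is to the completeness of safety capture and to descriptive attribution by modality. No endpoint or planned test is affected. How many events would be lost or misplaced cannot be estimated, because the documents give no rate of delayed onset and do not show the form.

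The conclusion assumes that the schedule is followed as written and that no unlisted safety contact exists. This is a cheap improvement, not a flaw that threatens the study's aims.

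**What to change.** Keep the after-session form and make four additions:

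1. Before stimulation at visit 7, add a short adverse-event item covering the time since the last session, with onset date.
2. Send the same form by REDCap link at the end of the two weeks after visit 11.
3. Send it also to anyone who stops early.
4. State that events are listed by the modality of the last session before onset. This is a timing convention, not a judgement of cause.

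Pre-session items at visits 3 to 6 and 8 to 11 are not needed: the modality is unchanged from the preceding session, and that day's after-session form can pick up the event.

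The cost is one short item at an existing visit and one automated send per participant. Data and Specimen Banking already describes timed sends and tracking. No visit is added. The downside is a small participant burden, plus staff time to review and follow up a few extra, mostly minor reports.

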### **Sources of materials**

Research materials to be obtained from participants:

Urine specimens will be collected at the screening visit to check for illicit drug use. In addition, women of childbearing potential will be required to have a urine pregnancy test at screening visit ensure a negative result (testing required by our MR unit; these tests will be disposed of at the visit).

### **Research data collected from participants:**

There are several types of data that we will be collecting: brain images; self-report questionnaire measures; and physical, psychological, and physiological parameters. In addition, clinical and demographic data will be obtained, including: complete information regarding descriptors of the participants' back pain (duration, frequency and magnitude of pain, etc) as well as a general medical history including surgical and treatment history, disability status, drinking and drug use, demographics, smoking status, height and weight. For all participants, the smartphone app will be used to monitor medication use, ratings of back pain intensity (NRS), mood and mobility, twice daily until the end of the study participation

### **Questionnaires used for assessing characteristics of cohorts:**

- **Personal Health History (PHH):** This general questionnaire will assess demographic information (gender, age, marital/relationship status, race/ethnicity, and education), pain history (descriptions, diagnostic testing history, and treatment history), general health history (other medical/surgical history, concurrent medications, health behaviors, a general symptom

STU#:

checklist, and health-care utilization), and work history. The entire questionnaire will be completed at the visit 1. Subjects will be asked about any changes to concurrent medications at subsequent visits. History and physical examination will be done to confirm diagnosis, inclusion and exclusion criteria and assess overall safety.

- **Vitals measurements:** blood pressure, heart rate, respiration rate, height and weight will be measured.
- **PainDETECT (PD-Q):** A 12-item self-report instrument that assesses neuropathic pain properties and was originally developed in a sample of 8,000 low back pain sufferers in Germany. The PD-Q demonstrates high sensitivity (80%) and specificity (85%) and has since been validated in other clinical pain populations. Although this instrument has not been validated in OA populations, it has been widely used in numerous OA studies.
- **Beck Depression Inventory, second version (BDI-II):** A 21-item self-report instrument for measuring the severity of depression in adults. It is well validated in pain populations and has been extensively used in pharmacological research.
- **Short-form Montreal Pain Questionnaires (sfMPQ):** A well-validated pain measure, which permits separation of sensory and affective components of pain, as well as a total pain score. It also includes a numeric/descriptor scale, a visual analog pain scale (VAS), and a body map to localize the pain. This instrument is very well validated and often used in pharmacological research. However, its affective subscale is thought to be relatively rudimentary. It will be used to track development or continuation of pain, as well as post-surgical pain.
- **Numerical Rating Scale (NRS):** is an 11-point numerical rating scale used to measure pain intensity, where 0 corresponds to no pain and 10 indicates worst possible pain. The timeframe in question is concerned with the average pain experienced at the moment, in the past 24hrs, or average over past week. This questionnaire has been extensively used across pain management studies.
- **NIH PROMIS-57 Profile:** This 57-item questionnaire contains brief scales for anxiety, depression, fatigue, pain interference, pain intensity, physical function, sleep disturbance, and the ability to participate in social roles. Each scale was created using PROMIS methodology and calibrated using item response theory.
- **Pain Catastrophizing Scale (PCS):** The PCS is a 13-item instrument derived from definitions of catastrophizing described in the literature as well as items from the catastrophizing subscale of the CSQ. The PCS instructions ask participants to reflect on past painful experiences, and to indicate the degree to which they experienced each of 13 thoughts or feelings when experiencing pain, on 5-point scales with the end points (0) not at all and (4) all the time. The PCS yields a total score and three subscale scores assessing rumination, magnification and helplessness. The PCS has been shown to have adequate to excellent internal consistency (coefficient alphas: total PCS = .87, rumination = .87, magnification = .66, and helplessness = .78).
- **Global impression of change (PGIC):** this questionnaire reflects a patient's belief about the efficacy of treatment. Although widely used in chronic pain clinical trials, PGIC's validity has not been formally assessed. PGIC is a 7 point scale depicting a patient's rating of overall improvement.

STU#:

- **Description of smartphone PainApp:** All participants will also use a smartphone app to log their back-pain intensity, their mood, their mobility and medication use and other information that they may wish to report. The smartphone data are entered every day during the study and after termination of treatment until the final study visit. Smartphone entries are immediately transmitted through Wi-Fi to a secure web site, downloaded daily to assess compliance, and stored in a second secure server (we have been using such apps for about 6 months and they have been very effective).

Procedures	Visit 1	Visit 2,3,4 5,7,8,9,10	Visits 6 and 11
Informed consent process	X		
Inclusion/exclusion criteria	X		
Demographic survey and patient information criteria	X		
Pregnancy test (if applicable) 	X	X 	
Drug urine test	X		
Vitals measurements	X		
Personal Health History (PHH)	X		
General physical exam	X		
BDI	X		
MRI	X		X 
Pain Detect Questionnaire (Pdq)	X		X
Short-form Montreal Pain Questionnaires (sfMPQ)	X		X
Pain Catastrophizing Scale (PCS)	X		
NIH PROMIS-57 Profile	X		
Randomization	X		
rTMS stimulation		X	X
NRS before/after stimulation		X	X
NRS average pain			X
Adverse events questionnaire		X	X
PainApp (During all the study) 	X	X	X
Approximate visit duration	2-3 hrs	1-2 hrs	1-2 hrs

**Table 1:** Related Procedures and Study Schema. Visits 1 through 10 will be completed according to the presented schema. 1. There is no specific recommendation for or against pregnancy, however, since this study will be utilizing Repetitive TMS as a mode of intervention, we will take the conservative approach and exclude pregnancy. Female subjects of childbearing potential will be asked to take a pregnancy test. If the pregnancy test is positive, the subject may not enroll in the study. Pregnancy test will be repeated in visits 2 and 8 (every ~ 2 weeks).

STU#:

2. Visit 6 and 11: These visits will be separated in two parts: part 1: last day of stimulation (stimulation + questionnaires) and part 2: MRI (at least 24hrs after part 1). For group 1, only visit 6 will have 2 parts and for group 2 only visit 11 (see Figure 1 for details).
3. PainApp: participants will be instructed to use our smartphone-based app to report pain intensity (NRS, where 0 is no pain and 10 is worst imaginable pain), mobility (minimum, average, maximum), mood (NRS, where -10 is sad and +10 is happy), and medication use, collected twice daily from Visit 1 until the end of participation).

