#### **Stimulation modality sequences:**

The order of the stimulation modalities will be different across subjects. Subjects will be randomly assigned to one of two possible groups/stimulation sequences (fig 1). Before enrollment starts, we will produce 18 envelopes containing the stimulation sequence (see below possible combinations; we expect to use only 16). The stimulation sequence will be kept in sealed envelopes; therefore, subjects will get their assignment according to the order of entrance in the study. The study coordinator will retain the original sequence list which will be kept in a locked place. The study staff who provides the stimulation TMS session will be the only un-ed personnel.

STU#:

[figure not shown]

Figure 1: Study design and stimulation sequence. The subjects will be allocated to 1 envelop according to the entrance in the study. All participants will receive all the 2modalities of stimulation. Each round is composed by 5 daily session of stimulation, participants will not know which round is active and which is sham. Participants randomized to group 1 will have a second MRI at visit 6; and participants randomized to group 2 at visit 11.

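### Table 1 footnote 1 puts the second repeat pregnancy test at visit 8, one day after round 2 of stimulation starts at visit 7; probably a visit-numbering slip.

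*Combined protocol and SAP*

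**What the plan says.** Table 1 has a pregnancy test at visit 1 and, in the column shared by visits 2-5 and 7-10, a further mark that refers to footnote 1. Only the footnote says which of those visits carry a test: "Pregnancy test will be repeated in visits 2 and 8 (every ~ 2 weeks"). It links the exclusion of pregnancy to the stimulation: "There is no specific recommendation for or against pregnancy, however, since this study will be utilizing Repetitive TMS as a mode of intervention", the protocol continues, "we will take the conservative approach and exclude pregnancy".

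The calendar comes from other places:

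- The text on visits 2-11 starts stimulation at visit 2 and gives ten sessions in all: "5 consecutive daily sessions of each stimulation round following the prior stimulation sequence order, interleaved by 2 weeks of wash out period".
- The Figure 1 legend agrees on the length of a round: "Each round is composed by 5 daily session of stimulation, participants will not know which round is active and which is sham".
- Table 1 footnote 2 describes visits 6 and 11 as having two parts, the first being "part 1: last day of stimulation (stimulation + questionnaires").
- On the lead-in from visit 1, the MRI Scan section says of participants: "They will be asked to use the pain app for the next 7-10 days prior to the first round of intervention".

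**The concern.** A repeat test meant to prevent stimulation during pregnancy should come before stimulation resumes. The visit 2 test does this for round 1, because visit 2 is the first day of that round. The matching visit for round 2 is visit 7, but the footnote names visit 8.

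What is at stake is a safety precaution that the protocol itself calls conservative. Staff who follow the footnote will give one round 2 session before the retest. The question does not touch any endpoint, the sample size or the analysis.

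**Working it through.** **Inputs.** First stimulation at visit 2; ten sessions, five consecutive days per round; two weeks of washout between rounds (text on visits 2-11; Study Timelines). Last stimulation days at visits 6 and 11 (Table 1, footnote 2). Visit 1 to visit 2 about 7-10 days (MRI Scan section). Repeat tests at visits 2 and 8, about every 2 weeks (Table 1, footnote 1).

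**Which visits form each round.** Five daily sessions from visit 2 give visits 2-6, and footnote 2 confirms that visit 6 closes a round. The next five visits are 7-11, and footnote 2 confirms that visit 11 closes the other round. Visit 7 is the first day of round 2 and visit 8 is the second. This does not need Figure 1, which is missing from the text available.

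**Day count.** Let visit 2 be day 0, so visits 2-6 are days 0-4. The two-week washout can be counted in three ways:

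| Reading of the washout | Visit 7 | Visit 8 |
|---|---|---|
| 14 days from visit 6 to visit 7 | 4 + 14 = day 18 | day 19 |
| 14 full days without stimulation | 4 + 15 = day 19 | day 20 |
| Same weekday as visit 2, two full weeks off | 4 + 17 = day 21 | day 22 |

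Visit 8 is one day after round 2 starts under every reading.

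**Checking the stated interval.** The gap between the two repeat tests is 19-22 days, or 19/7 = 2.7 to 22/7 = 3.1 weeks, so the footnote's figure is not reproduced. Visit 7 would give 18-21 days, or 2.6 to 3.0 weeks. Measured against 14 days, visit 8 is 5-8 days late and visit 7 is 4-7 days late. Days 5-17 hold no stimulation visit under any reading, so no scheduled visit falls 14 days after visit 2.

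If the visit 1 test is included, the gaps between the three tests are about 7-10 and 19-22 days. Their mean is (7 + 19)/2 = 13 to (10 + 22)/2 = 16 days, although neither gap alone is close to 14.

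**Sessions affected.** If the visit 8 test is done before that day's stimulation, one session (visit 7) precedes the retest and four (visits 8-11) follow it. The footnote does not state the order within the day.

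**How many have an active visit 7 session.** Only the sequence that receives hippocampal stimulation second does. The allocation ratio is not stated. The protocol says of the envelopes: "we will produce 18 envelopes containing the stimulation sequence (see below possible combinations; we expect to use only 16"). If the 18 are split 9:9 (an assumption), the 2 unused could both come from one sequence, so each sequence has between 9 - 2 = 7 and 9 participants. That counts everyone in the sequence. Only those of childbearing potential matter here, and the documents do not give their number.

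**The case against.** The strongest reply is that no stated rule is broken. The footnote does not require a test before each round; that intent is inferred from the visit 2 test alone. This stands, and it is why the slip can only be called probable. Some support comes from other apparent leftovers of a different design: three rounds and M1 stimulation in the intervention section, six sequences in the MRI Scan section, and a Table 1 caption that stops at visit 10 in an 11-visit study.

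A second reply is that the interval hardly separates the two visits. Visit 7 also misses two weeks, and the average gap over all three tests is 13-16 days, so the phrase could be a loose average. This also stands. The interval does not point to visit 7; it simply gives no reason for visit 8.

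A third reply is that the Sources of Materials section gives a different reason for testing, a requirement of the MR unit. For that purpose visit 7 or visit 8 would do equally well before group 2's second scan, after visit 11. But that passage concerns the screening test, whereas footnote 1 gives the use of rTMS as its reason.

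Finally, the protocol has a more serious pregnancy inconsistency. Risks to Participants says that a patient who is or may be pregnant is not excluded, while the Exclusion Criteria list pregnancy. That needs its own correction, but it does not make the visit 8 date right.

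**Conclusion.** The point holds and is minor. That visit 8 is the second day of round 2 follows from the protocol's own visit structure and does not depend on how the washout is counted. That visit 8 was unintended is likely but inferred.

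The size is one stimulation session, given on a test 18-21 days old, in participants of childbearing potential. This assumes that the visit 8 test precedes that day's session and that no visit is missed. The session is sham for one of the two sequences. The range of 7-9 of 16 with an active session rests on the assumed 9:9 split of envelopes; without it no firm bound can be given. The tests at visits 1 and 2 have already been done, and the visit 8 test still covers the later sessions, so the safety consequence is small.

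**What to change.** Replace the last sentence of footnote 1 with:

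> The pregnancy test is repeated at visits 2 and 7, before the first stimulation session of each round (about 3 weeks apart).

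This puts the retest ahead of the exposure it guards against, fixes the order within the day, and gives an interval that matches the calendar (18-21 days). Wording tied to the first session also helps with missed visits. Participants may miss one stimulation visit per round, and as the footnote stands, a missed visit 8 leaves no named round 2 visit for the test.

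The cost is one sentence. The number of tests is unchanged (visit 1 plus two repeats), no visit is added, and visit 7 is already in the same Table 1 column as visit 8. If the investigators did intend visit 8, the footnote should say why.
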